16.10. Appendix 10: Pharmacokinetic / Pharmacodynamic Methodology

Concentration-time profiles of GSK2330811 in plasma and Total OSM in serum, will be analysed by population pharmacokinetic/pharmacodynamic (PopPK/PD) methods using a non-linear mixed-effects modelling approach.

The objective of this analysis is to develop population PK/PD models that characterize the concentration-time profile of GSK2330811 and total OSM following repeated subcutaneous administration of GSK2330811 in patients with dcSSc.

Concentration-time profiles of GSK2330811 in plasma and platlets and haemoglobin will be analysed by PK/PD methods using a non-linear mixed-effects modelling approach. All the available exposure haematology clinical data relative to GSK2330811 will be combined for the analysis. This pooled analysis will be performed as a separate analysis and reported separately.

Analysis of clinical endpoints and biomarkers could include exposure-response, longitudinal exposure-response and joint modelling. This analysis would be performed after SAC, based on the results of the statistical analysis.

16.10.1. Systems

The quantitative analysis will be performed using NONMEM (ICON Solutions) and PsN (Perl Speaks NONMEM) or another software platform deemed appropriate. Graphical displays and, if needed, modifications of the dataset will be produced using R (The R Foundation for Statistical Computing). The analysis will be performed by, or under the direct auspices of, Clinical Pharmacology Modelling and Simulation (CPMS), GlaxoSmithKline using the GSK modelling environment MAP (Model-based Analysis Platform) using the currently supported versions of all software packages.

16.10.2. Data Assembly

GSK Stats and Programming will generate the NONMEM input dataset, as detailed in Section 16.9.1.

16.10.3. Model Development

A population PK/PD model for SC single dose of GSK2330811 in healthy volunteers was developed [Reid J, 2018] and will be the starting point for the population PK/PD analysis.

Individual parameters (empirical Bayes estimates) will be derived applying the HV popPKPD model to the repeat dose in dcSSc dataset with the MAXEVAL=0 option, if \$EST METHOD=1, or with the EONLY=1 option, if \$EST METHOD=IMP. If the corresponding model diagnostics indicate that the HV popPKPD model is appropriate to represent the dcSSc PKPD data, then these individual parameters for the dcSSc population will be considered adequate to characterise the PK/PD.

201247

If the parameter set of the HV popPKPD model applied to the dcSSc data set results in substantial bias or if a further exploration of the covariate effect in the dcSSc population is deemed necessary, the parameters of the HV popPKPD model will be re-estimated for the dcSSc PK/PD data alone and/or for a pooled HV (study 201246, study 208564 cohort 1) /dcSSc (study 201247) data set. If a pooled analysis is deemed necessary, it will be performed as a separate analysis and reported separately.

201247

16.11. Appendix 11: Abbreviations & Trade Marks

16.11.1. Abbreviations

Abbreviation	Description
AE	Adverse Event
A&R	Analysis and Reporting
AUC	Area under the (Concentration-Time) Curve
CI	Confidence Interval
CPMS	Clinical Pharmacology Modelling & Simulation
CRP	C-Reactive Protein
CRISS	Composite Response Index in diffuse cutaneous Systemic Sclerosis
CS	Clinical Statistics
CSR	Clinical Study Report
CTCAE	Common Terminology Criteria for Adverse Events
DBF	Database Freeze
DBR	Database Release
dcSSc	Diffuse Cutaneous Systemic Sclerosis
DOB	Date of Birth
DP	Decimal Places
DRC	Data Review Committee
ECG	Electrocardiogram
eCRF	Electronic Case Record Form
ELF	Enhanced Liver Fibrosis
EPO	Erythropoietin
FDAAA	Food and Drug Administration Clinical Results Disclosure Requirements
FVC	Forced Vital Capacity
GSK	GlaxoSmithKline
HAQ-DI	Health Assessment Questionnaire Disability Index HAQ-DI
IA	Interim Analysis
ICH	International Conference on Harmonization
IDSL	Integrated Data Standards Library
IMMS	International Modules Management System
IP	Investigational Product
MMRM	Mixed Model Repeated Measures
mRSS	modified Rodnan skin score
OSM	Oncostatin M
PCI	Potential Clinical Importance
PD	Pharmacodynamic
PDMP	Protocol Deviation Management Plan
PK	Pharmacokinetic
PP	Per Protocol
PopPK	Population PK
QC	Quality Control
QTcF	Friderica's QT Interval Corrected for Heart Rate
QTcB	Bazett's QT Interval Corrected for Heart Rate

201247

Abbreviation	Description
RAP	Reporting & Analysis Plan
RAMOS	Randomization & Medication Ordering System
RSE	Relative standard error
SAC	Statistical Analysis Complete
SD	Standard Deviation
SE	Standard Error
SDTM	Study Data Tabulation Model
TA	Therapeutic Area
TFL	Tables, Figures & Listings
TPO	Thrombopoietin

16.11.2. Trademarks

Trademarks of the GlaxoSmithKline
Group of Companies

None

Trademarks not owned by the GlaxoSmithKline Group of Companies

NONMEM

PsN SAS

201247

16.12. Appendix 12: List of Data Displays

16.12.1. Data Display Numbering

The following numbering will be applied for RAP generated displays:

Section	Tables Figures		
Study Population	1.1 to 1.32	NA	
Safety (incl. immunogenicity)	3.1 to 3.36	3.1 to 3.16	
Pharmacokinetic	4.1	4.1 to 4.8	
Population Pharmacokinetic (PopPK)	5.1 to 5.2	5.1 to 5.3	
Pharmacodynamic	6.1 to 6.4	6.1 to 6.6	
Pharmacokinetic / Pharmacodynamic	7.1 to 7.2	7.1 to 7.4	
Biomarker	8.1 to 8.23	8.1 to 8.25	
Exploratory Efficacy	9.1 to 9.22	9.1 to 9.23	
Section	Listings		
ICH Listings 1 to 34) 34	
Other Listings	35 t	o 51	

16.12.2. Mock Example Shell Referencing

Non IDSL specifications will be referenced as indicated and if required example mock-up displays will be provided in a separate document.

Section	Figure	Table	Listing
Study Population	POP_Fn	POP_Tn	POP_Ln
Efficacy	EFF_Fn	EFF_Tn	EFF_Ln
Safety	SAFE_Fn	SAFE_Tn	SAFE_Ln
Pharmacokinetic	PK_Fn	PK_Tn	PK_Ln
Population Pharmacokinetic (PopPK)	POPPK_Fn	POPPK_Tn	POPPK_Ln
Pharmacodynamic and / or Biomarker	PD_Fn	PD_Tn	PD_Ln
Pharmacokinetic / Pharmacodynamic	PKPD_Fn	PKPD_Tn	PK/PD_Ln
Biomarker	BIO_Fn	BIO_Tn	BIO_Ln

NOTES:

Non-Standard displays are indicated in the 'IDSL / Example Shell' or 'Programming Notes' column as '[Non-Standard] + Reference.'

16.12.3. Deliverables

Delivery [Priority] ^[1]	Description
SRT	Safety Review Team
DEC	Dose Escalation
DECX	Expanded Dose Escalation [conditional on DEC decision]. Note that all outputs created for DEC will also be produced for DECX unless specified. Depending on the reason for expansion this RAP may be further developed for the DECX interim.
IA1	Interim Analysis 1 Statistical Analysis Complete
	("Target Engagement" interim)

201247

Delivery [Priority] [1]	Description
IA2	Interim Analysis 2 Statistical Analysis Complete
	("Baseline biomarker" interim)
Adhoc DRC	Statistical Analysis Complete at request of the data review committee (DRC)
SAC	Final Statistical Analysis Complete

NOTES: Indicates priority (i.e. order) in which displays will be generated for the reporting effort, priority may not be specified

For interim analyses, not all outputs produced for the interim will automatically be shared in the meeting. For example, if it is not necessary to review individual level data then, although this may have been produced, it will not be reviewed by the DRC. Also, as described above, outputs from the preceding SRT may be shared at any interim but note that the data cut for the SRT may be at a different time than the data cut for the DEC and that SRT outputs may be produced from data that has not been cleaned by data management.

16.12.4. Study Population Tables

Study	Study Population Tables						
No.	Population	IDSL / TST ID / Example Shell	Title	Programming Notes	Deliverable		
Dispo	osition						
1.1.	Safety	ES1	Summary of Subject Disposition	Include Total Column	SAC		
1.2.	Screened	ES6	Summary of Screening Status and Reasons for Screen Failures		SAC		
1.3.	Safety	SD1	Summary of Treatment Status and Reason for Discontinuation of Study Treatment	Include Total Column	SAC		
1.4.	Enrolled	NS1	Summary of Number of Subjects by Country and Centre ID	PLS Requirement	SAC		
1.5.	Per Protocol	NS1	Summary of Number of Subjects by Country and Centre ID	PLS Requirement	SAC		
Proto	col Deviations	S					
1.6.	Safety	DV1	Summary of Important Protocol Deviations not Related to COVID-19		SAC		
1.7.	Safety	DV1	Summary of Important Protocol Deviations Related to COVID-19		SAC		
Popu	lations Analys	sed					
1.8.	Screened	SP1	Summary of Study Populations		IA1, IA2, SAC		
1.9.	Safety	SP2	Summary of the Exclusions from the Per Protocol Population	Include programmatical exclusions specified in Section 16.1.1.	SAC		
Demo	Demography						
1.10.	Safety	DM1	Summary of Demographic Characteristics		IA1, IA2, Adhoc DRC, SAC		
1.11.	Per Protocol	DM1	Summary of Demographic Characteristics	Only produce if per-protocol population is different from the safety population.	SAC		

Study	udy Population Tables						
No.	Population	IDSL / TST ID / Example Shell	Title	Programming Notes	Deliverable		
1.12.	Enrolled	DM11	Summary of Age Ranges		SAC		
1.13.	Safety	DM6	Summary of Race and Racial Combination Details		IA2, Adhoc DRC, SAC		
Disea	ise characteri	stics					
1.14.	Safety	POP_T1	Summary of Systemic Sclerosis Disease History		IA1, IA2, SAC		
1.15.	Safety	POP_T2	Summary of Systemic Sclerosis Medication History		IA1, IA2, SAC		
1.16.	Safety	POP_T2	Summary of Concomitant Mycophenolate		IA1, IA2, SAC		
1.17.	Safety	POP_T3	Summary of Historical Autoantibody Profile		IA1, IA2, SAC		
1.18.	Safety	POP_T3	Summary of Baseline Autoantibody Profile		SAC		
1.19.	Safety	EFF_T1	Summary of DLCO (mL/min/mmHg) at Screening	By treatment, Include corrected and uncorrected for Hb.	SAC		
1.20.	Per Protocol	POP_T1	Summary of Systemic Sclerosis Disease History	As for Table 1.12. Only produce if per-protocol population is different from the safety population.	SAC		
1.21.	Per Protocol	POP_T2	Summary of Systemic Sclerosis Medication History	As for Table 1.13. Only produce if per-protocol population is different from the safety population.	SAC		
1.22.	Per Protocol	POP_T2	Summary of Concomitant Mycophenolate	As for Table 1.14. Only produce if per-protocol population is different from the safety population.	SAC		

Study	Study Population Tables						
No.	Population	IDSL / TST ID / Example Shell	Title	Programming Notes	Deliverable		
1.23.	Per Protocol	POP_T3	Summary of Baseline Autoantibody Profile	As for Table 1.16. Only produce if per-protocol population is different from the safety population.	SAC		
1.24.	Per Protocol	EFF_T1	Summary of DLCO (mL/min/mmHg) at Screening	By treatment, Include corrected and uncorrected for Hb. Only produce if per- protocol population is different from the safety population.	SAC		
1.25.	Per Protocol	POP_T4	Summary of Mycophenolate use at Day 1	If biomarker analysis will be done by safety population, use safety population here.	SAC		
Conc	Concomitant Medications and Medical Conditions						
1.26.	Safety	MH1	Summary of Current/Past Medical Conditions other than Systemic Sclerosis		SAC		
1.27.	Safety	CM8	Summary of Concomitant Medications by Ingredient and Ingredient Combinations		IA1, IA2, SAC		
1.28.	Safety	SU1	Summary of Smoking History		SAC		

Study	udy Population Tables							
No.	Population	IDSL / TST ID / Example Shell	Title	Programming Notes	Deliverable			
Ехро	sure							
1.29.	Safety	POP_T5	Summary of Treatment Compliance	Add footnotes: '[1] Includes subjects who attended the study visit and a dose was withheld, it does not include subjects who missed dosing visits.' 'Note: Percentages use n as denominator'.	SAC			
1.30.	Per Protocol	POP_T5	Summary of Treatment Compliance	Add footnotes: '[1] Includes subjects who attended the study visit and a dose was withheld, it does not include subjects who missed dosing visits.' 'Note: Percentages use n as denominator'.Only produce if per-protocol population is different from the safety population.	SAC			
1.31.	Safety	POP_T6	Summary of Exposure to Study Treatment		SAC			
1.32.	Per Protocol	POP_T6	Summary of Exposure to Study Treatment	Only produce if per-protocol population is different from the safety population.	SAC			

16.12.5. Safety Tables

Safety: Tables						
No.	Population	IDSL / TST ID / Example Shell	Title	Programming Notes	Deliverable	
Adverse	e Events					
3.1.	Safety	AE1	Summary of All Adverse Events by System Organ Class and Preferred Term, by Treatment Phase	For IA1, don't present by phase and remove ', by Treatment Phase' from the title. Add a row to include number of participants contributing to treatment phase and use as denominator. Add footnote 'Note: On treatment phase defined as period from first dose to last dose + 28 days. Follow up phase defined as period after last dose + 28 days.'	IA1, IA2, Adhoc DRC, SAC	
3.2.	Safety	AE3	Summary of Common (>=5%) Adverse Events, by Treatment Phase	Add a row to include number of participants contributing to treatment phase and use as denominator. Add footnote 'Note: On treatment phase defined as period from first dose to last dose + 28 days. Follow up phase defined as period after last dose + 28 days.'	SAC	
3.3.	Safety	AE15	Summary of Common (>=5%) Non-serious Adverse Events by System Organ Class and Preferred Term (Number of Subjects and Occurrences)		SAC	
3.4.	Safety	AE5A	Summary of Adverse Events by System Organ Class and Preferred Term and Maximum Intensity, by Treatment Phase	Add a row to include number of participants contributing to treatment	SAC	

Safety:	Safety: Tables						
No.	Population	IDSL / TST ID / Example Shell	Title	Programming Notes	Deliverable		
3.5.	Safety	AE1	Summary of Drug-Related Adverse Events, by Treatment Phase	phase and use as denominator. Add footnote 'Note: On treatment phase	SAC		
3.6.	Safety	AE5A	Summary of Drug-Related Adverse Events by System Organ Class and Preferred Term and Maximum Intensity, by Treatment Phase	defined as period from first dose to last dose + 28 days. Follow up phase defined as period after last dose + 28 days.'	SAC		
3.7.	Safety	AE3	Summary of Non-Serious Drug-Related Adverse Events, by Treatment Phase		SAC		
Serious	AEs	I					
3.8.	Safety	AE1	Summary of Non-Fatal Serious Adverse Events, by System Organ Class, by Treatment Phase	Add a row to include number of participants contributing to treatment phase and use as denominator. Add footnote 'Note: On treatment phase defined as period from first dose to last dose + 28 days. Follow up phase defined as period after last dose + 28 days.'	SAC		
3.9.	Safety	AE1	Summary of Serious Adverse Events by System Organ Class and Preferred Term, by Treatment Phase	For IA1, don't present by phase and remove ', by Treatment Phase' from the title. Add a row to include number of participants contributing to treatment phase and use as denominator. Add footnote 'Note: On treatment phase defined as period from first dose to last dose + 28 days. Follow up phase defined as period after last dose + 28 days.'	IA1, IA2, SAC		

Safety: Tables						
No.	Population	IDSL / TST ID / Example Shell	Title	Programming Notes	Deliverable	
3.10.	Safety	AE16	Summary of Serious Adverse Events by System Organ Class and Preferred Term (Number of Subjects and Occurrences)		SAC	
3.11.	Safety	AE3	Summary of Serious Drug-Related Adverse Events, by Treatment Phase	Add a row to include number of participants contributing to treatment phase and use as denominator.	SAC	
3.12.	Safety	AE1	Summary of Adverse Events Leading to Permanent Discontinuation of Study Treatment or Withdrawal from Study by System Organ Class and Preferred Term, by Treatment Phase	Add footnote 'Note: On treatment phase defined as period from first dose to last dose + 28 days. Follow up phase defined as period after last dose + 28 days.'	SAC	
3.13.	Safety	AE3	Summary of Non-Fatal Drug-Related Serious Adverse Events, by Treatment Phase	Add a row to include number of participants contributing to treatment	SAC	
3.14.	Safety	AE3	Summary of Fatal Drug-Related Serious Adverse Events, by Treatment Phase	phase and use as denominator. Add footnote 'Note: On treatment phase defined as period from first dose to last dose + 28 days. Follow up phase defined as period after last dose + 28 days '		
Chemis	try					
3.15.	Safety	LB1	Summary of Chemistry		IA1, IA2, SAC	
3.16.	Safety	LB1	Summary of Change from Baseline in Chemistry		IA1, IA2, SAC	
3.17.	Safety	LB1	Summary of Percentage Change from Baseline in Chemistry		IA1, IA2, SAC	
3.18.	Safety	LB17	Summary of Worst-Case Chemistry Results Relative to Potential Clinical Importance (PCI) Criteria Post-Baseline Relative to Baseline		DEC, SAC	
Haemat	ology					

Safety:	Tables				
No.	Population	IDSL / TST ID / Example Shell	Title	Programming Notes	Deliverable
3.19.	Safety	SAFE_T1	Summary of Blinded Haematology	Blinded dataset. Page by cohort. By Parameter, this output should be produced for the blinded safety parameters (Table 3 in Section 3.1.1.2). These are: Platelet Count, Haemoglobin, Haematocrit, RBC count For SRTs, include date of the central lab data cut.	SRT, DEC
3.20.	Safety	SAFE_T1	Summary of Change from Baseline – Blinded Haematology	Blinded dataset. Page by cohort. By Parameter, this output should be produced for the blinded safety parameters Table 3 in Section 3.1.1.2). These are: Platelet Count, Haemoglobin, Haematocrit, RBC count For SRTs, include date of the central lab data cut.	SRT, DEC
3.21.	Safety	SAFE_T3	"[Blinded] Summary of Platelet Count and Anaemia Events by CTCAE Grade [and cohort]	By Parameter / event. Just Haemoglobin (anemia) and Platelet count decrease For SRT use 'Blinded' i.e. do not report treatment code but do report cohort (i.e. cohort 1 and cohort 2) For Interims and final do use treatment code, do not use cohort.	SRT IA1, IA2, Adhoc DRC, SAC

Safety:	Safety: Tables							
No.	Population	IDSL / TST ID / Example Shell	Title	Programming Notes	Deliverable			
3.22.	Safety	SAFE_T4	Summary of Haematological Limits Crossed During Study	Haemoglobin, report two events: <80 g/L (permanent discontinuation), <90g/L (repeat test) Platelets, report three events: <50 GI/L,(permanent discontinuation) >=50 GI/L & <75 GI/L (temporary discontinuation) and <100 GI/L (repeat test)	SAC			
3.23.	Safety	LB1	Summary of Haematology	By parameter	IA1, IA2, Adhoc DRC, SAC			
3.24.	Safety	LB1	Summary of Haematology Change from Baseline	By parameter	IA1, IA2, Adhoc DRC, SAC			
3.25.	Safety	LB1	Summary of Percentage Change from Baseline in Haematology	By parameter	IA1, IA2, Adhoc DRC, SAC			

Safety:	Safety: Tables							
No.	Population	IDSL / TST ID / Example Shell	Title	Programming Notes	Deliverable			
3.26.	Safety	LB16	Summary of Haematology Results by Maximum CTCAE Grade Increase Post-Baseline Relative to Baseline	Add Footnote: [1] CTCAE grade determined using laboratory values only as defined in V4.03: June 14, 2010 and does not take into account the clinical context. Note: Subjects are counted in Increase to Grade 1, 2, 3 and 4 by comparing the baseline grade to the maximum post baseline grade. Increase to Grades 1 to 4 is by adding number of subjects in Increase to Grade 1, 2, 3, and 4. Increase to Grades 2 to 4 is by adding number of subjects in Increase to Grade 2, 3 and 4. Increase to Grades 3 to 4 is by adding number of subjects in Increase to Grade 3 and 4."	IA1, IA2, Adhoc DRC, SAC			
3.27.	Safety	SAFE_T5	Summary of Nadirs for Selected Haematology Parameters	Haematology parameter group 1 only. by parameter, treatment group.	IA1, IA2, Adhoc DRC, SAC			
3.28.	Safety	SAFE_T5	Summary of Nadirs for Selected Haematology Parameters as Percent Change from Baseline	Do not produce for Reticulocytes (i.e. produce for Haemoglobin, Red Blood Cells, Platelets and Absolute Neutrophil Counts only). Footnote: "Nadir is the lowest post-baseline value of the parameter including local lab results. Haematology Group 1 Parameters: Haemoglobin, Red Blood Cells, Platelet Count and Absolute Neutrophil Counts."	DEC, IA1, IA2, Adhoc DRC, SAC			
3.29.	Safety	SAFE_T6	Summary of Days to Nadir of Selected Haematology Parameters		DEC, IA1, IA2, SAC			
Urinaly	sis							
3.30.	Safety	SAFE_T7	Summary of Emergent Worst Case Urinalysis Results		IA1, IA2, SAC			

201247

Safety: Tables							
No.	Population	IDSL / TST ID / Example Shell	Title	Programming Notes	Deliverable		
ECG							
3.31.	Safety	EG1	Summary of ECG Findings		IA1, IA2, SAC		
3.32.	Safety	EG2	Summary of ECG Values	"Note: If multiple assessments collected	IA1, IA2, SAC		
3.33.	Safety	EG2	Summary of Change from Baseline in ECG Values by Visit	in any clinical visits then the mean of the multiple values within the assessments has been used in the summary."	IA1, IA2, SAC		
Vital Sig	gns	·		·			
3.34.	Safety	VS1	Summary of Change from Baseline in Vital Signs by Visit		IA1, IA2, SAC		
3.35.	Safety	VS7	Summary of Vital Sign Results Relative to Potential Clinical Importance (PCI) Criteria Post-Baseline Relative to Baseline		IA1, IA2, SAC		

16.12.6. Immunogenicity Tables (may be categorised under Safety in HARP folder structure / SAFIRE naming)

Immuno	Immunogenicity: Tables							
No.	Population	IDSL / TST ID / Example Shell	Title	Programming Notes	Deliverable			
Immuno	Immunogenicity							
3.36.	Safety	IMM1	Summary of Positive Immunogenicity results	Add footnote: Note: The denominator for confirmed positive is the total number of subjects at that visit who have immunogenicity data available.	SAC			

16.12.7. Safety Figures

Safety:	Safety: Figures							
No.	Population	IDSL / TST ID / Example Shell	Title	Programming Notes	Deliverable			
Adverse	e Events							
3.1.	Safety	AE10	Plot of Top 20 Adverse Events and Relative Risks	Top 20 AE by overall number of events. Add following footnote and use in programming rules: "Note: Top 20 Adverse Events by overall number of events displayed and the AE has to have at least 1 occurrence in the placebo group for relative risk to be calculated. Only AEs with calculated relative risk are displayed."	SAC			
Chemis	try							
3.2.	Safety	BIO_F2	Mean Profile for Chemistry Results by Treatment Group	For Haptoglobin, Ferritin, Vitamin B12 and Folate. Add footnote "Figure displays a subset of Chemistry parameters"	SAC			
3.3.	Safety	BIO_F4	Subject Profiles for Chemistry Results by Treatment Group		SAC			

Safety: Figures						
No.	Population	IDSL / TST ID / Example Shell	Title	Programming Notes	Deliverable	
Haemat	ology					
3.4.	SRT Safety	SAFE_F2	Minimum Value at Each Visit – Blinded Haematology	By Haematology parameter, this output should be produced for the blinded safety parameters (Table 3 in Section 3.1.1.2). These are: Platelet Count, Haemoglobin, Haematocrit, RBC count Show relevant CTCAE grades as reference lines on y axis. The relevant boundary is the highest- grade level that the lowest lab value is above (e.g. if the lowest values are just above grade 2, then show grade 2). Where grade depends on individual demographics (e.g. age, sex) show the highest boundary that applies to the analysis population.	SRT, DEC	
3.5.	SRT Safety	SAFE_F2	Greatest Reduction from Baseline at Each Visit – Blinded Haematology	By Haematology parameter, this output should be produced for the blinded safety parameters (Table 3 in Section 3.1.1.2). These are: Platelet Count, Haemoglobin, Haematocrit, RBC count Scatter plot, one point per planned visit. Include 0 on y-axis	SRT, DEC	

Safety:	Safety: Figures							
No.	Population	IDSL / TST ID / Example Shell	Title	Programming Notes	Deliverable			
3.6.	Safety	201246/final/ Figure 3.1	Participant Profiles of Haematology by Treatment Group	By Haematology parameter, this output should be produced for the blinded safety parameters (Table 3 in Section 3.1.1.2) with the exception of Haematocrit. i.e. for: Platelet Count, Haemoglobin, RBC count Do not show grade 1 boundary. Show grade 2 boundary (or higher) as described for output 3.2 if any participant exceeds grade 1. X axis use 'Actual relative time' from dose. Show all observed values including unscheduled.	DEC ^[1] , IA1 ^[1] , IA2 ^[1]			
				of haematology parameters"	Adboc DBC			
3.7.	Safety	BIO_F4	Subject Profiles for Haematology by Treatment Group	For SAC for Haematology parameter	SAC			
3.8.	Safety	BIO_F4	Subject Profiles for Percentage Change from Baseline Haematology by Treatment Group	group 1, Red Cell Distribution Width and mean platelet volume. Use rules for CTCAE boundaries for Figure 3.7 X axis use 'Time (Days)' from dose. Show all observed values including unscheduled. Add footnote "Figure displays a subset of haematology parameters"	Adhoc DRC, SAC			
3.9.	Safety	BIO_F2	Mean Profile for Haematology by Treatment Group	By Haematology parameter. For IA1 and IA2 for Haematology	IA1, IA2, Adhoc DRC, SAC			

Safety:	Safety: Figures							
No.	Population	IDSL / TST ID / Example Shell	Title	Programming Notes	Deliverable			
3.10.	Safety	BIO_F2	Mean Percentage Change from Baseline for Haematology by Treatment Group	parameter group 1. For SAC, Haematology parameter group 1, Red Cell Distribution Width and mean platelet volume. X axis shows visits with approximate temporal spacing Add footnote "Figure displays a subset of haematology parameters"	IA1, IA2, Adhoc DRC, SAC			
3.11.	Safety	PK_F1	Scatter Plot of Platelet Nadir vs. Haemoglobin Nadir	Panel by treatment group and grouped by individual subjects X-axis Label: Platelet Nadirs Y-axis Label: Haemoglobin Nadirs	SAC			
Hepato	biliary (Liver)							
3.12.	Safety	LIVER14	Scatter Plot of Maximum vs. Baseline for ALT		SAC			
3.13.	Safety	LIVER9	Scatter Plot of Maximum ALT vs. Maximum Total Bilirubin		SAC			
3.14.	Safety	201246/final/ Figure 3.9	LFT Patient Profiles	Single plot combining the following parameters: ALT = Alanine Amino Transferase, AST = Aspartate Amino Transferase, Alk. Phos. = Alkaline Phosphatase,Total Bili. = Total Bilirubin	SAC			
ECG								

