10. STATISTICAL CONSIDERATIONS

10.1. Sample Size Determination

No formal sample size calculations have been conducted as the sample size is based on feasibility.

The primary objective is safety and tolerability, where for cohort 1 an initial cohort of four participants will be randomised to either GSK2330811 or placebo in a 3:1 ratio. In cohort 2 a minimum of approximately 20 and a maximum of 36 participants will be randomised to GSK2330811 or placebo in a 3:1 ratio.

[Table 3](#) illustrates the credible interval for observed safety events in the GSK2330811 group in cohorts 1 and 2. This uses a Bayesian approach assuming a non-informative conjugate prior distribution Beta(1,1). This illustrates that if one event in three participants is observed, for example, then a true rate of 0.806 for that safety event cannot be ruled out.

Table 3 Inferences on the true event rate

Study Cohort	Observed event rate (events / treated participants)	Upper limit of 95% credible interval for the true event rate
Cohort 1 (N=3)	0/3	0.602
	1/3	0.806
	2/3	0.932
	3/3	0.994
Cohort 2 (N=15)	0/15	0.206
	1/15	0.302
	2/15	0.383
	3/15	0.456

For information, for the exploratory endpoint of fibrosis log (PIIINP) assuming an SD=0.521 (Lee, 2001) and a sample size of 15 participants receiving GSK2330811 and 5 receiving placebo, it is estimated that the lower and upper bounds of the 95% confidence interval for the comparison of GSK2330811 to Placebo will be within 0.565 of the point estimate. This calculation is based on a two tailed Type I error rate of 5%. The difference in log (PIIINP) between healthy volunteers and Systemic Sclerosis patients was 0.42 in an observational study (Lee, 2001).

Within the defined range, the final number of participants recruited may depend on an interim sample size re-estimation.

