10.3. Statistical Analyses

10.3.1. Safety Analyses

All safety analyses will be performed on the Safety Population.

Endpoint	Statistical Analysis Methods
Primary and Secondary	
No formal statistical testing will be performed on safety data.
 
If deemed appropriate posterior probabilities of the true rate of an adverse event of interest may be calculated using a non-informative prior distribution.
 
Clinical interpretation will be based upon review and displays of adverse events, disease related events, laboratory values and vital signs. The principal consideration in this evaluation will be the investigator-reported relationships of either adverse events or laboratory abnormalities to investigational product.
 
Safety data including immunogenicity data will be presented in tabular and/or graphical format and summarized descriptively according to GSK's Integrated Data Standards Library (IDSL) standard.
 
Target Engagement will be presented in tabular and graphical format and summarized descriptively according to GSK's IDSL standard for Pharmacodynamic endpoints.
 
Sparse blood sampling is being implemented in this study to allow the full pharmacokinetic profile for each participant to be reconstructed using Bayesian prediction from a population pharmacokinetic model using Non Linear Mixed Effect Model (NONMEM) version VII or higher and determine the exposure over the dosing interval (AUC (0- τ)), apparent systemic clearance (CL/F), and apparent volume of distribution (Vss/F).
 
Plasma GSK2330811 concentration data will be presented in tabular and graphical format and summarized descriptively according to GSK's IDSL standards.

Exploratory	Will be described in the reporting and analysis plan (RAP).

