5. CONSIDERATIONS FOR DATA ANALYSES AND DATA HANDLING CONVENTIONS

5.1. Study Treatment Display Descriptors

Treatment Group Descriptions			
RandAll NG Data Displays for Reporting			
Code	Description ^[3]	Description ^[2] Order ^[1]	
А	GSK2230811 100 mg SC - PARALLEL	GSK2330811 100 mg	2
В	GSK2230811 300 mg SC - PARALLEL	GSK2330811 300 mg	3
Р	Placebo - PARALLEL	Placebo	1

NOTES:

1. Order represents treatments being presented in TFL, as appropriate.

2. If there is no space for the full drug name, and the full drug name is in the title or elsewhere on the output then the dose amount (i.e. 100mg or 300mg) may be used with consultation with statistician

3. This RAP instruction corrects a mistake in the Treatment Description field in the RANDALL NG.

Treatment comparisons will be displayed as follows using the descriptors as specified:

- 1. GSK2330811 100 mg vs Placebo
- 2. GSK2330811 300 mg vs Placebo

Or, in short form when full drug name is shown in title or elsewhere on table, listing or Figure and after consultation with statistician:

- 1. 100 mg vs Placebo
- 2. 300 mg vs Placebo

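### SAP Figure 3.1 shows an adverse event only if it occurred on placebo, so an event seen only on GSK2330811 cannot appear in it

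*SAP*

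**What the plan says.** Figure 3.1 in SAP section 16.12.7 plots AEs with their relative risks, on the Safety population, using shell AE10, for the final analysis only. The ranking rule is "Top 20 AE by overall number of events". The programming note then gives a footnote and tells the programmer to apply it as a rule. An AE must have "at least 1 occurrence in the placebo group for relative risk to be calculated. Only AEs with calculated relative risk are displayed".

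SAP section 5.1 names the two treatment comparisons, one of which is "GSK2330811 300 mg vs Placebo", and shows placebo as a single group.

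Protocol section 10.3.1 plans no formal testing of safety data. It states that "Clinical interpretation will be based upon review and displays of adverse events, disease related events, laboratory values and vital signs", with investigator-reported relationship to study drug as the principal consideration.

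The other AE outputs state no placebo condition. In SAP section 16.12.5 these include Table 3.1, "Summary of All Adverse Events by System Organ Class and Preferred Term, by Treatment Phase", and Table 3.5, "Summary of Drug-Related Adverse Events, by Treatment Phase". Listing 15 lists all AEs.

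**The concern.** A relative risk with zero placebo cases is undefined, and that is a good reason to leave the ratio blank. It is not a reason to delete the AE. The rule deletes it, and it works in one direction. Zero cases on placebo removes an AE. Zero cases on GSK2330811 gives a relative risk of 0, which can be calculated, so that AE stays eligible. The rows removed are those with the most extreme excess on active treatment.

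Safety and tolerability is the primary objective, and interpretation rests on displays rather than tests. Among the AE displays I could see, Figure 3.1 is the only one that names a between-arm measure. (Part of the listings section was not available to me, and the AE10 shell is not reproduced in the SAP.) A reader using the figure to compare arms would miss active-only AEs that are among the most frequent in the trial. The footnote tells that reader that AEs may be absent, but not which ones or how many.

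**Working it through.** **The rule.** No arithmetic is needed for the main point. No placebo case means no relative risk, and no relative risk means no row. An active-only AE has probability 0 of being displayed. The plan gives no figure of its own to reproduce here.

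**Size of the placebo group.** Cohort 1 starts with four people (protocol section 10.1). For the second cohort the same section plans that "a minimum of approximately 20 and a maximum of 36 participants will be randomised to GSK2330811 or placebo in a 3:1 ratio". The allocation ratio is the same in both, so placebo is a quarter of each total.
- Minimum: 4 + 20 = 24 randomised, so 18 active and 6 placebo.
- Maximum: 4 + 36 = 40 randomised, so 30 active and 10 placebo.

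**Chance that an AE has no placebo case.** P = (1 − p)^n, with p the true placebo rate and n the placebo size. The documents give no AE rates, so p is an assumed range. For example, 0.95^6 = 0.735.

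| Placebo rate p | n = 6 | n = 10 |
|---|---|---|
| 5% | 0.735 | 0.599 |
| 10% | 0.531 | 0.349 |
| 20% | 0.262 | 0.107 |
| 30% | 0.118 | 0.028 |

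**Without assuming a rate.** If treatment has no effect and k participants have the AE, the chance that all are on active is C(active, k) / C(total, k).

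| k affected | 18 v 6 | 30 v 10 |
|---|---|---|
| 1 | 0.750 | 0.750 |
| 2 | 0.554 | 0.558 |
| 3 | 0.403 | 0.411 |
| 5 | 0.202 | 0.217 |

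So even an AE unrelated to treatment and seen in five people is left out about one time in five.

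**Restricting to frequent AEs.** The figure concerns the top 20, so I conditioned on at least 4 affected participants, a rough proxy for frequency. P(no placebo case | at least 4 affected) = P(at least 4 on active) × (1 − p)^n / P(at least 4 in total), by exact binomial enumeration.

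| True rate, active v placebo | 18 v 6 | 30 v 10 |
|---|---|---|
| 5% v 5% | 27% | 26% |
| 10% v 10% | 24% | 21% |
| 20% v 20% | 18% | 10% |
| 30% v 30% | 10% | 3% |
| 33% v 5% | 72% | 60% |

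For the last row at 18 v 6: 0.6565 / 0.9131 = 0.719. Counting active participants in cohort 2 only (15 v 6 and 27 v 10) gives 21/19/15/9% and 23/19/9/3% for the equal rates, and 70% and 60% for the last row.

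**Simulating the ranking rule.** The SAP ranks by events, not participants, so I simulated that too, with 20,000 trials per setting. Assumptions: 40, 60 or 80 background AE terms with incidence drawn from Beta(1, 9) (mean 10%), equal in both arms; one further AE at 33% v 5%; and a Poisson number of extra events with mean 0, 0.5 or 1 per affected participant. Each trial takes the top 20 by total events, breaks ties at random, then drops rows with no placebo case.
- The 33% v 5% AE, when it ranks in the top 20, is dropped in about 71 to 73% of trials at 18 v 6 and about 58 to 60% at 30 v 10.
- On average about 4 to 7 of the 20 ranked rows are dropped at 18 v 6, and about 2 to 4 at 30 v 10.
- Placebo-only AEs in the top 20 average 0.0 to 0.5 rows.

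**The case against.** The strongest reply is that nothing is lost. Tables 3.1 to 3.14 and Listing 15 have no placebo condition, and Table 3.2 already gives the common AEs. Protocol section 10.3.1 puts most weight on investigator-reported relationship, which the drug-related tables serve. The expected falls in platelets and haemoglobin have their own unfiltered laboratory displays. The filter is disclosed in the footnote, the figure is produced once, and limiting a relative-risk plot to AEs that have a relative risk is a recognisable convention. All of that stands, and it limits the importance of the point. It does not make the figure sound, because the footnote neither names nor counts what is missing, and what is missing lies in one direction.

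Three narrower points also stand.
- Every rate above is assumed.
- The SAP does not say whether the top 20 is taken before or after the filter. If after, other AEs fill the empty places and the count of dropped rows no longer applies; active-only AEs are absent under either order.
- The AE10 shell is not shown, so how it would draw a relative risk of 0 is unknown. Placebo-only AEs seldom reach the top 20 in any case, so the practical effect is the missing active-only rows, not an excess of placebo-only ones.

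**Conclusion.** The concern holds. As written, Figure 3.1 cannot show an AE that occurred only on GSK2330811, and with about 6 to 10 placebo participants this will affect real rows. The exclusion follows from the rule alone. How often it happens depends on the assumed placebo rate: from 74% (6 participants) or 60% (10) at 5%, down to 12% or 3% at 30%. This is a fault in one final-analysis display. It changes no estimate, no planned decision and no other AE output. It should be corrected because safety is the primary objective and the correction is nearly free.

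**What to change.** In the Figure 3.1 programming note and footnote, remove the sentence that limits the display to AEs with a calculated relative risk, and remove placebo occurrence as a condition for display. Rank all AEs by overall number of events and keep every top-20 AE, with n/N by treatment group. Where placebo has no case, print the relative risk as not estimable. If the AE10 shell already shows n/N by group, that part needs no change.

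The cost is one programming note, one footnote and one figure shell. It needs no new data or analysis, and no interim output is affected because the figure is delivered only at the final analysis. A risk difference with an exact or Newcombe interval for each comparison in SAP section 5.1 would be a useful option, but it is an added analysis and is not needed to correct the fault.
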